Efficacy Analyses: The number and percentage of subjects with investigator assessment of clinical response will be presented at each time point (EOT and PTE). The number and percentage of subjects who achieve clinical stability will be presented for each day, EOT and PTE.

Rationale for Number of Subjects: This study is designed to evaluate the PK profile of an oral dosing regimen, BID on Day 1 and QD on Day 2, in adults with CABP. The sample size determination is based on consideration of the precision of the estimate, GMR of $AUC_{(0-48)}$ for 300mg po to 100mg IV, derived from model-based simulations of omadacycline concentration data (Phase I studies).

With 20 evaluable subjects, there will be 90% probability that the 90% CIs of the GMR for $AUC_{(0-48)}$ will be within 80% and 125%. Up to 30 subjects will be enrolled so that at least 20 subjects are evaluable for bioavailability estimation. The number may be adjusted as needed to meet this requirement.

TABLE OF CONTENTS

SY	NOPSI	S	2
TA	BLE O	F CONTENTS	11
LIS	ST OF 7	ΓABLES	14
LIS	ST OF A	APPENDICES	14
LIS	ST OF A	ABBREVIATIONS AND DEFINITIONS OF TERMS	15
1	DISC	LOSURE STATEMENT	18
2	CON	TACTS	19
	2.1	Emergency Contacts	19
	2.2	Additional Contacts	19
3	INTR	ODUCTION	20
	3.1	Community Acquired Bacterial Pneumonia	20
	3.2	Omadacycline	20
4	STUI	DY OBJECTIVES	20
	4.1	Primary Objective	20
	4.2	Secondary Objectives	21
	4.3	Exploratory Objectives	21
5	INVE	STIGATIONAL PLAN	22
	5.1	Overall Study Description	22
	5.2	Rationale for Study Design	22
	5.3	Approximate Duration of Subject Participation	23
	5.4	Approximate Duration of Study	23
	5.5	Approximate Number of Subjects	23
6	STUI	DY POPULATION SELECTION	24
	6.1	Study Population	24
	6.2	Inclusion and Exclusion Criteria	24
	6.3	Screen Failures	27
7	STUI	DY TREATMENT(S)	28
	7.1	Treatments Administered	28
	7.2	Identity of the Investigational Product: Omadacycline	28
	7.3	Dose Selection Rationale	28
	7.4	Description of Treatments	29
	7.5	Test Article Administration	29
	7.5		
		7.5.1.1Management While on Oral Test Article	
	7.6	Dose Adjustments and Interruptions of Test Article	
	7.6	5 6	
	7.7	Dispensing Test Article	30

	7.8		and Concomitant Therapy	
	7.9		ibited Therapy	
	7.10		nitted Treatments	
	7.11		tment Compliance	
	7.12	Pack	aging and Labeling	31
	7.13	Stora	age and Accountability	31
	7.14	Inve	stigational Product Retention at Study Site	31
8	STU	DY Pl	ROCEDURES	32
	8.1	Info	med Consent	32
	8.2	Subj	ect Demographics/Other Baseline Characteristics	32

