6.2 Inclusion and Exclusion Criteria

Each subject must meet all of the following criteria to be enrolled in this study:

Main Criteria for Inclusion:

- 1. Written and signed informed consent must be obtained before any protocol specific assessment is performed.
- 2. Male or female, age 18 years or older.
- 3. Has at least 3 of the following symptoms:
 - Cough
 - Production of purulent sputum
 - Dyspnea (shortness of breath)
 - Pleuritic chest pain
- 4. Has at least TWO of the following abnormal vital signs:
 - Fever or hypothermia documented by the investigator (temperature > 38.0°C [100.4°F] or < 36.0°C [95.5°F])
 - Hypotension with systolic blood pressure (SBP) < 90 mm Hg
 - Heart rate > 90 beats per minute (bpm)
 - Respiratory rate (RR) > 20 breaths/minute
- 5. Has at least 1 clinical sign or laboratory finding associated with CABP:
 - Hypoxemia (partial pressure of arterial oxygen [PaO₂] < 60 mm Hg by arterial blood gas [ABG] or oxygen saturation < 90% by pulse oximetry)
 - Physical examination findings of pulmonary consolidation (eg, dullness on percussion, bronchial breath sounds, or egophony)
 - An elevated total white blood cell (WBC) count (> 12,000 cells/mm³) or leucopenia (WBC < 4,000 cells/mm³) or elevated immature neutrophils (> 15% band forms), see % bands calculation in Appendix 2 (regardless of total peripheral WBC count)
- 6. Has disease categorized as being PORT Risk Class II or III at Screening where initiation of antibiotics with oral therapy is appropriate in the opinion of the investigator, whether inpatient or outpatient setting (see PORT Risk Class calculation in Appendix 4).

- 7. Radiographically-confirmed pneumonia, ie, new or progressive pulmonary infiltrate(s) on chest X-ray (CXR) or chest computed tomography (CT) scan consistent with acute bacterial pneumonia within 48 hours prior to the first dose of test article.
- 8. Ability to swallow up to 3 tablets in succession.
- 9. Females must have a negative urine pregnancy test at Screening and agree to comply with using an acceptable method of birth control as per your local requirements (eg, abstinence, oral contraceptive, intrauterine device [IUD], barrier contraception [condom], tubal ligation, hysterectomy, bilateral oophorectomy, postmenopausal, or vasectomized partner) from Screening through PTE. Males must agree to use an acceptable method of birth control with female partner(s) and must not donate sperm from Screening through PTE.

Main Criteria for Exclusion:

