8.12.2 Clinical Stability

The formal determination of the subject's Clinical Stability will be done programmatically using the investigator's assessment of the subject's vital signs entered into the eCRF. The investigator is not responsible for categorizing the subject's Clinical Stability. Clinical Stability will be determined daily and analyzed by day, EOT, and PTE.

Patients will be considered clinically stable if they achieve all of the following criteria:

- temperature $\leq 37.8^{\circ}C (100^{\circ}F);$
- heart rate ≤ 100 beats/minute;
- RR \leq 24 breaths/minute;
- systolic blood pressure \geq 90 mmHg; and
- arterial oxygen saturation $\ge 90\%$ or PaO2 ≥ 60 mmHg on room air.

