9.2 Clinical Stability

The formal determination of the subject's Clinical Stability will be done programmatically using the investigator's assessment of the subject's vital signs entered into the eCRF. The investigator is not responsible for categorizing the subject's Clinical Stability. Clinical Stability will be determined daily and analyzed by day, early clinical response window, EOT, and PTE.

Patients will be considered clinically stable if they achieve all the following criteria:

- temperature $\leq 37.8^{\circ}$ C (100°F);
- heart rate ≤ 100 beats/minute;
- RR \leq 24 breaths/minute;
- systolic blood pressure \geq 90 mmHg; and
- arterial oxygen saturation $\ge 90\%$ or PaO2 ≥ 60 mmHg on room air.

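### Clinical Stability limits for heart rate, respiratory rate and low temperature are looser than the entry limits, so some subjects can be stable before dosing and still be counted as achieving stability

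*Protocol*

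**What the plan says.** **Entry.** Protocol 6.2, criterion 4, reads "Has at least TWO of the following abnormal vital signs". The four signs are temperature above 38.0°C or below 36.0°C, systolic blood pressure (SBP) below 90 mm Hg, heart rate above 90, and "Respiratory rate (RR) > 20 breaths/minute". Criterion 5 asks for one further finding. Hypoxemia is only one of three ways to meet it; consolidation on examination or an abnormal white cell or band count also suffices.

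**Endpoint.** Protocol 8.12.2 says "Patients will be considered clinically stable if they achieve all of the following criteria", and SAP 9.2 says "Patients will be considered clinically stable if they achieve all the following criteria". Both then list the same limits: temperature 37.8°C or less, heart rate 100 or less, respiratory rate 24 or less, SBP 90 or more, and saturation at least 90% or PaO2 at least 60 mmHg on room air.

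**Reporting.** The Protocol Synopsis, Efficacy Analyses, says: "The number and percentage of subjects who achieve clinical stability will be presented for each day, EOT and PTE". SAP 9.2 adds an early clinical response window. Neither document requires a subject to be unstable at baseline, sets apart those already stable, or tabulates the composite before dosing.

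**Related tables.** SAP 6.2 summarizes the abnormal baseline signs one at a time. SAP 9.3 plans an EOT table in the intent-to-treat (ITT) population with tighter limits: no fever or hypothermia, SBP above 90, heart rate below 90 and respiratory rate below 20.

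**The concern.** A percentage of subjects who achieve stability is normally read as the share who moved from unstable to stable on treatment. If some met the rule on arrival, the figure combines response with the way subjects were selected. The study has one arm, so no control group shows how large the second part is.

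The early days are the most exposed. Appendix 1 of the protocol schedules all five signs on Day 1, and blood pressure and heart rate are also taken within 30 minutes before dosing. Neither 8.12.2 nor SAP 9.2 says which Day 1 reading feeds the rule.

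At stake is the interpretation of an exploratory efficacy summary. The protocol does use this kind of figure: section 5.2 supports the shorter treatment duration with a Day 7 result above 80% for symptom improvement and clinical stability in the earlier Phase 3 study.

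**Working it through.** The plan states no figure for this endpoint, so there is none to reproduce. The check compares the two sets of limits.

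**Step 1: limits side by side**

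| Sign | Abnormal for entry (Protocol 6.2) | Stable (Protocol 8.12.2, SAP 9.2) | Values that are both |
|---|---|---|---|
| Heart rate | > 90 | ≤ 100 | 91–100 |
| Respiratory rate | > 20 | ≤ 24 | 21–24 |
| Low temperature | < 36.0°C | no lower bound | all below 36.0°C |
| Fever | > 38.0°C | ≤ 37.8°C | none |
| SBP | < 90 | ≥ 90 | none |
| Oxygenation | saturation < 90% or PaO2 < 60 | saturation ≥ 90% or PaO2 ≥ 60 | same cut-offs |

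**Step 2: which entry pairs are compatible with stability.** Four signs give six pairs. The three that include SBP below 90 fail the stability rule. The other three can pass: heart rate 91–100 with respiratory rate 21–24, hypothermia with heart rate 91–100, and hypothermia with respiratory rate 21–24. All three signs together can also pass. No subject entering with fever can.

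**Step 3: an eligible example.** Take a man of 60 with heart rate 95, respiratory rate 22, temperature 37.0°C, SBP 120, saturation 95%, white cell count 13,000, three of the listed symptoms and a confirmed infiltrate. By Protocol Appendix 4 he scores 60 for age and nothing for these signs, which is Class II (51–70) if no other points apply. He meets inclusion criteria 3 to 5 and 7, and the risk-class part of criterion 6. He also meets all five stability criteria before any dose.

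**Step 4: exhaustive check.** Cutting the signs at the stated limits gives 4 temperature, 3 SBP, 4 heart-rate, 4 respiratory-rate and 2 oxygenation bands. Of the resulting combinations, 240 have at least two abnormal entry signs.

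- Already stable under Protocol 8.12.2: 12 of 240.
- Already stable under the SAP 9.3 vital-sign limits: 0 of 240.

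These count combinations of bands, not patients.

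**Step 5: possible size.** Let p be the share stable before dosing, s the share of those still stable at a visit, and r the share of the rest who are stable then.

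Reported rate = p·s + (1 − p)·r, which is at most p + (1 − p)·r (when s = 1). The excess over r is then p(1 − r).

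The documents give none of p, s or r. With assumed r = 60% and s = 1:

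- p = 10%: 0.10 + 0.90 × 0.60 = 0.64, an excess of 4 points.
- p = 30%: 0.30 + 0.70 × 0.60 = 0.72, an excess of 12 points.

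Among 30 enrolled subjects, these values of p mean 3 to 9 people. With assumed r = 80% the same range gives 0.10 + 0.90 × 0.80 = 0.82 to 0.30 + 0.70 × 0.80 = 0.86, an excess of 2 to 6 points.

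**The case against.** The best defense is that 8.12.2 defines a state at each visit, not a change from baseline, and a stability rule need not mirror diagnostic entry criteria. The item is exploratory, and Protocol 12.8 plans no formal comparisons. This largely stands and keeps the point minor. It does not remove it, because the Synopsis reports subjects who achieve stability, and that invites the change reading.

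The second defense is that the plan already holds relevant information. SAP 9.3 has the stricter EOT table, SAP 6.2 the baseline signs, SAP 8.2 the changes in vital signs, and SAP section 5 lists all data for what will be about 30 subjects. This also stands in part. A reader might infer that nothing in the plan separates response from eligibility, and these sections show that to be too strong. But SAP 9.3 covers EOT only, and SAP 6.2 counts signs singly at the entry cut-offs, so the composite at 100 and 24 cannot be recovered from its table.

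Third, the size is assumed, and sampling error may exceed it: at 60% with n = 30 the 95% half-width is 1.96 × √(0.6 × 0.4/30) = 17.5 points. That is correct, but the excess over r has a systematic part that more subjects would not remove.

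**Conclusion.** The point holds in a limited form. For heart rate, respiratory rate and low temperature, values that qualify a subject for entry can also satisfy the stability rule, and no planned table shows how many subjects meet the composite before dosing.

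Four stronger readings are not supported:

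- **That the stability limits are looser throughout.** The fever limit is stricter, SBP is complementary at 90, and oxygenation uses the same cut-offs.
- **That 64% to 72% is a forecast.** It is the upper bound for assumed values of p and r, with every pre-stable subject staying stable. Nor is 12 of 240 a patient proportion.
- **That the documents fix the denominator as ITT.** Protocol 12.6.2 attaches ITT to the investigator's assessment and then lists Clinical Stability as a key assessment; SAP 9.3 states ITT for its own EOT table. For the by-day and PTE stability percentages, ITT is the natural inference but is not stated.
- **That the main result is affected.** The pharmacokinetic analysis and the sample size do not use this endpoint.

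The overlap itself rests only on the documents' thresholds. Its effect on the reported rate depends on the unknown case mix. This is a worthwhile refinement of an exploratory summary.

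**What to change.** 1. Apply the programmed 8.12.2 rule to the last pre-dose values, as SAP 10.2.5 defines baseline, and tabulate the number and percentage already stable. Screening values alone are the wrong anchor, because blood pressure and heart rate are measured again shortly before the first dose.
2. Beside the all-subject percentages by day, at EOT and at PTE, give the percentages among subjects not stable at baseline.
3. State the analysis population for Clinical Stability, and say which Day 1 reading is used.
4. Reconcile SAP 9.2 and 9.3, which set different limits for stability side by side, or name them as two separate measures.

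The vital signs needed are already scheduled, so no visit or procedure is added. One item needs checking: the rule refers to room air, and neither Protocol 8.5 nor Appendix 1 says that room-air status is recorded. The post-dose determinations have the same need. The cost is one baseline row, one added set of percentages, and a smaller denominator for that set.

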8.13 Adverse Events

An AE is any untoward, undesired, or unplanned event in the form of signs, symptoms, disease, or laboratory or physiologic observations occurring in a person given a test article or in a clinical study. The event does not need to be causally related to the test article or clinical study. An AE includes, but is not limited to, the following:

- Any clinically significant worsening of a preexisting condition.
- An AE occurring from overdose of a test article, whether accidental or intentional. Overdose is a dose greater than that specified in the protocol.
- An AE occurring from abuse (eg, use for nonclinical reasons) of a test article.
- An AE that has been associated with the discontinuation of the use of a test article.

8.14 Serious Adverse Events

A serious adverse event (SAE) is an AE that:

- Results in death
- Is life-threatening (see below)
- Requires hospitalization or prolongation of an existing hospitalization (see below)
- Results in a persistent or significant disability or incapacity (see below)
- Results in a congenital anomaly or birth defect
- Additionally, important medical events that may not result in death, be life-threatening, or require hospitalization may be considered SAEs when, based on appropriate medical

judgment, they may jeopardize the subject and may require medical or surgical intervention to prevent any one (1) of the outcomes listed above in this definition. Examples of such events include allergic bronchospasm requiring intensive treatment in an emergency room or at home, blood dyscrasias, or convulsions that do not result in hospitalization, or development of drug dependency or drug abuse.

Life-threatening refers to immediate risk of death as the event occurred per the reporter. A life-threatening experience does not include an experience, had it occurred in a more severe form, might have caused death, but as it actually occurred, did not create an immediate risk of death. For example, hepatitis that resolved without evidence of hepatic failure would not be considered life-threatening, even though hepatitis of a more severe nature can be fatal. Similarly, an allergic reaction resulting in angioedema of the face would not be life-threatening, even though angioedema of the larynx, allergic bronchospasm, or anaphylaxis can be fatal.

Hospitalization is official admission to a hospital. Hospitalization or prolongation of a hospitalization constitutes criteria for an AE to be serious; however, it is not in itself considered an SAE. In absence of an AE, a hospitalization or prolongation of a hospitalization should not be reported as an SAE by the participating investigator. This is the case in the following situations:

- The hospitalization or prolongation of hospitalization is needed for a procedure required by the protocol.
- The hospitalization or prolongation of hospitalization is part of a routine procedure followed by the center (eg, stent removal after surgery). This should be recorded in the study file.
- A hospitalization for a preexisting condition that has not worsened.

Disability is defined as a substantial disruption in a person's ability to conduct normal life functions.

If there is any doubt about whether the information constitutes an SAE, the information is treated as an SAE.

8.15 Other Reportable Information

Certain information, although not considered an SAE, must be recorded, reported, and followed up as indicated for an SAE. This includes:

• Pregnancy exposure to a test article: If a pregnancy is confirmed, use of the test article must be discontinued immediately. Information about pregnancy exposure includes the entire course of pregnancy and delivery, and perinatal and neonatal outcomes, even if there are no abnormal findings. Both maternal and paternal exposures are considered other reportable information. For exposure involving the female partner of a male subject, the necessary information must be collected from the subject, while respecting the confidentiality of the partner.

- Lactation exposure to a test article with or without an AE.
- Overdose of a test article as specified in this protocol with or without an AE.
- Inadvertent or accidental exposure to a test article with or without an AE.

8.16 Overdose

Any administration of omadacycline of greater than 1350 mg within a 24-hour period will be an overdose, regardless of whether the overdose is intentional or accidental, it is a reportable event and the sponsor must be notified within 1 business day. The site personnel will retain this confirmation report.

The physician managing the overdose may order any test he/she thinks is necessary to manage the subject properly.

8.17 Medication Errors

Medication errors are the result of administration or consumption of the wrong product, by the wrong subject, at the wrong time, and/or by the wrong administration route, due to human error.

Medication errors include, but are not limited to, the following:

- The administration and/or consumption of test article that has not been assigned to the subject
- Administration of expired test article

All AEs and SAEs must be handled as specified in this protocol whether or not they are associated with a medication error. A medication error associated with an SAE (including overdose, inadvertent exposure, and/or accidental exposure) will be reported with the SAE on the SAE Report Form. All other medication errors will be reported by e-mailing the Clinical Test Article Error Incident Report Form as indicated in the Emergency Contacts (see Section 2).

8.18 Recording and Reporting

A subject's AEs and SAEs will be recorded and reported from the signing of the ICF to the time of the Final Follow-up assessment. The investigator must instruct the subject to report AEs and SAEs during this time period. Reports of death within 30 days after the last contact with the subject will be reported to the sponsor and additional information relative to the cause of death will be sought and documented.

All AEs and SAEs must be recorded on source documents. All AEs and SAEs for subjects who receive a treatment assignment will be recorded in the eCRFs.

The investigator must follow-up as medically necessary on all AEs and SAEs until the events have subsided, the condition has returned to Baseline, or in case of permanent impairment, until the condition stabilizes.

Adverse events should be based on the signs or symptoms detected during the physical examination and on clinical evaluation of the subject. In addition to the information obtained from those sources, the subject should be asked the following nonspecific question: "How have you been feeling since your last visit?" Whenever possible, AEs should be reported as a diagnosis rather than individual signs and symptoms. If a definitive diagnosis is not possible, the individual signs and symptoms should be recorded using standard medical terminology.

If an AE requires a surgical or diagnostic procedure, the illness leading to the procedure should be recorded as the AE, not the procedure itself.

Death should be recorded in the eCRF as an outcome of an AE. Any unanticipated risks to the subjects must be reported promptly to the IRB/IEC/REB.

8.18.1 Serious Adverse Event Reporting

All SAEs and follow-up information must be reported within 1 business day or 24 hours as required by local regulations by emailing a completed SAE Report to the email address below.

Serious Adverse Event (SAE) contact information: E-Mail:

8.18.2 Assessment of Relatedness

The investigator will assess causality (ie, whether there is a reasonable possibility that test article caused the event) for all AEs and SAEs. The relationship will be characterized using the following classification:

- Not related: This relationship suggests that there is no association between test article and the reported event. The event can be explained by other factors such as an underlying medical condition, concomitant therapy, or accident, and no plausible temporal or biologic relationship exists between test article and the event.
- Related: This relationship suggests that a definite causal relationship exists between test article administration and the AE, or there is a reasonable possibility that the event was caused by the study medication, and other conditions (concurrent illness, progression/expression of disease state, or concurrent medication reaction) do not appear to explain the event.

Adverse events and SAEs also will be assessed for their potential relationship to the protocol. A protocol-related AE is one that is not related to the test article but is considered by the investigator or the medical monitor (or designee) to be related to the research conditions, ie, related to the fact that a subject is participating in the study. For example, a protocol-related AE may be an untoward event related to a medical procedure required by the protocol.

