8.1 Adverse Events

Verbatim descriptions of AEs will be coded using Version 17.1 or higher of MedDRA. Summary tables will be provided for all treatment-emergent adverse events (TEAEs), but all AEs will be provided in a listing. A treatment-emergent AE is defined as any AE that newly appeared, increased in frequency, or worsened in severity on or after the initiation of active test article. An AE is considered treatment emergent if the AE start date and time is on or after the start date and time of the first dose of active test article. If time of the AE is missing and it occurred on the same date as the first dose of active test article, the AE will be defined as treatment emergent. If the start date of the AE is partial or missing and it cannot be determined if the AE occurred prior to or after the first dose of test article, the AE should be defined as treatment emergent.

An overall summary of AEs will include the number of subjects who experienced at least one AE of the following categories: any AE, any TEAE, any drug-related TEAE, any severe TEAE, any serious TEAE, any drug-related SAE, any serious TEAE leading to death, any TEAE leading to premature discontinuation of test article, any TEAE leading to premature discontinuation from the study, any TEAE leading to dose interruption of test article, and any serious TEAE leading to premature discontinuation of test article.

The number and percentage of subjects reporting a TEAE will be tabulated by system organ class and preferred term; by system organ class, preferred term, and severity (mild, moderate, and severe); and by system organ class, preferred term, and relationship (unrelated or related to test article). The incidence of TEAEs will be summarized by preferred term, sorted by decreasing frequency, for all TEAEs, related TEAEs, serious TEAEs, and TEAEs leading to study drug discontinuation. The incidence of serious TEAEs, TEAEs leading to premature discontinuation of test article, and TEAEs leading to a dose interruption of test article will be summarized by system organ class and preferred term. For all analyses of TEAEs, if the same AE (based on preferred term) is reported for the same subject more than once, the AE is counted only once for that preferred term and at the highest severity and strongest relationship to test article.

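### The two causality categories in Protocol 8.18.2 do not implement the section's own opening test: an event with a plausible drug link that another condition also appears to explain fits neither.

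*Protocol*

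**What the plan says.** Protocol 8.18.2 asks the investigator to judge, for every AE and SAE, "whether there is a reasonable possibility that test article caused the event". It then gives two categories.

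- *Not related* is introduced as the absence of an association. Two statements follow, joined by a conjunction. The first points to another cause: "The event can be explained by other factors such as an underlying medical condition, concomitant therapy, or accident". The second concerns the drug itself and requires that "no plausible temporal or biologic relationship exists between test article and the event".
- *Related* opens with two routes, a definite one and a weaker one: "This relationship suggests that a definite causal relationship exists between test article administration and the AE, or there is a reasonable possibility". Its closing clause adds that "other conditions (concurrent illness, progression/expression of disease state, or concurrent medication reaction) do not appear to explain the event".

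There is no intermediate level and no tie-break. The same section defines a protocol-related event as one that has first been judged not related to the test article.

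SAP 8.1 uses the same two levels. Its overall AE summary includes "any drug-related TEAE, any severe TEAE, any serious TEAE, any drug-related SAE". TEAEs are also tabulated by system organ class, preferred term and relationship, and related TEAEs by preferred term. A preferred term repeated within a subject is counted once, at the strongest relationship. SAP 10.1 states that causality may not be missing, and that a relationship which is nevertheless missing is taken as related.

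**The concern.** The opening sentence asks one question, and a two-level answer to it should be yes or no. Each definition instead adds a condition about other causes, and the added conditions are not mirror images. An event can therefore have a plausible drug link, which rules out *Not related*, and another apparent explanation, which rules out the reasonable-possibility route to *Related*.

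The setting makes such events credible. Every subject has acute pneumonia. Adjunctive systemic corticosteroids are allowed (Protocol 6.2, exclusion 8), and so are all treatments not listed as prohibited (Protocol 7.10). The alternatives named in the *Related* definition (illness, disease expression, other medication) are therefore present in the study population.

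What is at stake is the set of drug-related tables in SAP 8.1. The trial is open-label with one treatment group, so there is no concurrent control rate against which to check the investigators' attribution. About 5 sites would each settle the mixed cases in their own way. An ambiguous first decision also carries over to the protocol-related judgement, which depends on it.

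**Working it through.** The documents give no figure for this point, so the check is a logical enumeration of the wording in Protocol 8.18.2.

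**Inputs**

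- D: a definite causal relationship exists.
- P: a plausible relationship, or reasonable possibility, exists. The two phrases are treated as one condition, and D implies P.
- A: another condition appears to explain the event.

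**Formulas**

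- Opening test = P.
- *Not related* = A and not P.
- *Related*, reading (a), where the added condition attaches only to the reasonable-possibility route = D or (P and not A).
- *Related*, reading (b), where it attaches to both routes = (D or P) and not A.

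Three yes/no conditions give 8 combinations. Dropping the 2 in which D holds without P leaves 6.

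| D | P | A | Opening test | *Not related* | *Related* (a) | *Related* (b) |
|---|---|---|---|---|---|---|
| 0 | 0 | 0 | not met | no | no | no |
| 0 | 0 | 1 | not met | yes | no | no |
| 0 | 1 | 0 | met | no | yes | yes |
| 0 | 1 | 1 | **met** | **no** | **no** | **no** |
| 1 | 1 | 0 | met | no | yes | yes |
| 1 | 1 | 1 | met | no | yes | no |

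**Results**

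1. Under reading (a), 2 of 6 combinations have no category; under reading (b), 3 of 6. The categories are not exhaustive on either reading.
2. The row that matters is D=0, P=1, A=1. It meets the opening test and fails both definitions, however the *Related* sentence is parsed.
3. The row D=0, P=0, A=0 also fails both if every clause is treated as a strict requirement. However, *Not related* is introduced as the absence of an association, which arguably covers it. The point does not depend on this row.
4. Treating *plausible* and *reasonable possibility* as one condition does not create the gap. If plausibility is the weaker condition, any reasonable possibility is still plausible, so the mixed event still fails *Not related*.

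**Do the SAP rules close the gap?** No. Taking a missing relationship as related acts only on blanks, and causality may not be blank. The strongest-relationship rule acts only when the same preferred term recurs in a subject and another occurrence was marked related. Neither reclassifies a mixed event that the investigator has marked *Not related*.

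**Direction.** In the mixed row the opening test gives *Related*. Against that benchmark, a departure in this row can only lower the related count. Whether investigators depart from it at all is not known.

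**Scale per subject.** SAP 8.1 counts subjects. One subject whose status changes moves a drug-related percentage by 1/30 = 3.3 points with 30 treated subjects, or 1/20 = 5.0 points with 20. These denominators are assumptions based on the planned enrolment and the evaluable target. The number of subjects affected is not derivable.

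**The case against.** The other side has a good deal to say, and several stronger readings should be set aside.

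- **A reader might infer that any alternative explanation bars *Related*.** The text does not go that far. It bars *Related* only when other conditions appear to explain the event, which is a judgement about apparent cause and not about mere possibility. On the more natural reading, (a), a definite causal link stays *Related* regardless.
- **A reader might infer that drug-related events will be systematically under-counted.** The documents do not show this. The mixed event is excluded from *Not related* as plainly as from *Related*, and the opening test favours *Related*. An investigator who falls back on that test would classify as intended. Only the possibility of under-counting stands.
- **A reader might infer that mixed events are the usual case in CABP.** No figure supports this. Some disease-explained events never reach the causality question: worsening of the qualifying pneumonia is recorded as clinical failure unless it is serious (Protocol 8.18.5), and laboratory abnormalities become AEs only if clinically significant and outside what baseline and clinical course would lead one to expect (8.18.4). Chemistry is scheduled at Screening, EOT and PTE only (Appendix 1), so early laboratory events would come from unscheduled tests.
- **Much of the safety reporting does not use causality.** All TEAEs, serious TEAEs, and TEAEs leading to discontinuation or interruption are tabulated whatever their relationship, as are laboratory shifts and notable vital signs. Safety is a secondary, descriptive objective.

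All of this limits the consequence. None of it supplies a category for the mixed event, and the conservative SAP rules do not reach it.

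**Conclusion.** The point holds in a limited form. Protocol 8.18.2 states one test and then defines two mandatory categories that contradict it for events with both a plausible drug link and another apparent explanation. Sites must resolve these without a rule. Classification may therefore be inconsistent, and the drug-related TEAE and SAE counts in SAP 8.1 may fall below what the opening test would give.

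The size cannot be derived from the documents, and a downward bias is possible but not demonstrated. Total TEAE and SAE counts, and the primary PK analysis, are unaffected. The conclusion assumes that the clauses of each category are read as conditions to be met, and that the opening sentence states the intended test. The correction is worth making because the rule is wrong as written and cheap to repair.

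**What to change.** Rewrite the two definitions in Protocol 8.18.2 so that they are complementary and follow the opening sentence:

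- *Related*: it is reasonably possible that the test article caused the event, even if other factors may also have contributed.
- *Not related*: there is no such reasonable possibility.

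Delete from *Related* the condition that "other conditions (concurrent illness, progression/expression of disease state, or concurrent medication reaction) do not appear to explain the event". With *Related* = P and *Not related* = not P, each of the six combinations above falls in exactly one category and agrees with the opening test.

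The cost is two sentences in the protocol and a matching line in the eCRF completion guide. No data collection is added, and the two-level SAP tables stay as they are. The downside is that the reported drug-related AE percentage may be somewhat higher.
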